7.3.2.2 Sensitivity analyses

As a sensitivity analysis, missing data for participants in the mITT population will be imputed via MI. Twenty repeats of the imputation will be performed using Markov Chain Monte Carlo (MCMC) assuming non-monotone missing. Where the subject was discontinued due to lack of efficacy, due to an AE (with the exception of COVID-19), the subject has met the criteria for treatment failure as described in Section 7.3.3.4, or the subject's values are censored due to a prohibited therapy as described in Section 7.3.2.1, missing values will be imputed drawing from the baseline values, conditioned on the non-missing post-baseline values, of all participants in the mITT population under the assumption that they are missing not at random (MNAR); duration of leg pain will be included as a covariate.

If the study medication was discontinued for any other reason, values will be imputed within treatment group using MI under the assumption that they are missing at random (MAR) with covariates for duration of leg pain, and the weekly average worst leg pain score recorded at each time point (including baseline). The MAR approach will also be applied for sporadic missing values (prior to discontinuation). Values missing due to COVID-19, whether the result of early termination or sporadic missing values, are assumed MAR and unrelated to the endpoint of the weekly average VAS worst leg pain.

Data will be imputed for the full set of visits as described above and the same output will be used as a sensitivity for both the primary at Week 13 and the secondary endpoint at Week 52.

The MMRM analysis as described for the primary will be repeated for each of the 20 sets of data and combined using SAS PROC MIANALYZE. See Appendix [13.2](#) for the list of random seeds.

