7.3.2 Primary Efficacy Analyses

The change from baseline in the worst leg pain scores will be analyzed by a mixed model for repeated measures (MMRM) analysis for Week 1 through Week 52 in the mITT population. Records analyzed will be the weekly averages at Weeks 1, 2, 4, 6, 13, 26, 39, and 52 (see Section [7.3.2.1](#) for additional details).

The primary comparison will be the mean change from baseline of the SI-6603 group at Week 13 compared with the control group, estimated using this model. The model will include the baseline worst leg pain score, treatment, time, treatment-by-time interaction, and duration of leg pain as fixed effects.

An unstructured covariance will be used to model the covariance structure among repeated measures. Should the model fail to converge with the type = UN option, a compound symmetry structure will be used. Kenward-Roger method will be used for computing the denominator degrees of freedom. The missing data will be implicitly handled via a mixed-effect model, without explicit imputation.

The primary efficacy objective will be tested using the null hypothesis that there is no difference in the mean change from the pretreatment measure of pain relief (weekly average VAS worst leg pain) between SI-6603 and control at 13 weeks. This null hypothesis can be expressed as the hypothesis test

$H_0: \delta_{13} = 0$ vs. $H_A: \delta_{13} \neq 0$

where δ_{13} is the mean difference in the change from the pretreatment measure of pain relief (weekly average VAS worst leg pain) between SI-6603 and control at Week 13 from the model-based estimates of each treatment's change from pretreatment at those visits.

Worst leg pain score and change from baseline in worst leg pain score will be summarized by treatment group and time point. Mean change from baseline over time will be summarized in a line graph with error bars.

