7.3.3.2 Sensitivity Analyses for Key Secondary endpoints

An MI approach identical to that used for the sensitivity analysis for the primary endpoint will be applied for each key secondary endpoint. As with the primary, a full set of data will be imputed for all visits including Week 52 and the analyses will report results for both the Week 13 and Week 52 time points.

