13.2 Randomization Seeds

The following is the list of seeds to be used for any imputations; they will be used in the order that they appear in the production dataset. If the list below is insufficient for the number of seeds required, the list will repeat with values 1 greater than those given.

514895564
763527595
221543962
855875309
919252181
252975352
524264245
800238255
734425865
366652284

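### Twenty imputations leave avoidable Monte Carlo error in the missing-data sensitivity analysis; it matters only for borderline results and costs almost nothing to reduce

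*SAP*

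**What the plan says.** SAP 7.3.2.2 introduces the analysis in these terms: "As a sensitivity analysis, missing data for participants in the mITT population will be imputed via MI". Its size is then fixed: "Twenty repeats of the imputation will be performed using Markov Chain Monte Carlo (MCMC) assuming non-monotone missing". Values missing after discontinuation for lack of efficacy or an adverse event, after treatment failure, or after censoring for a prohibited therapy are drawn from the baseline distribution (missing not at random, MNAR). Other missing values are imputed within treatment group under missing at random (MAR). The MMRM "will be repeated for each of the 20 sets of data and combined using SAS PROC MIANALYZE". The same imputed data serve Week 13 and Week 52.

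SAP 7.3.3.2 extends this to the other confirmatory endpoints: "An MI approach identical to that used for the sensitivity analysis for the primary endpoint will be applied for each key secondary endpoint".

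Appendix 13.2 deals with seeds. It says "The following is the list of seeds to be used for any imputations", that "they will be used in the order that they appear in the production dataset", and that if the ten listed are too few, "the list will repeat with values 1 greater than those given".

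The primary test in SAP 7.3.2 uses no imputation: "The missing data will be implicitly handled via a mixed-effect model, without explicit imputation". The gatekeeping sequence in SAP 7.3.4 does not mention the MI results. SAP section 3 gives a general two-sided 0.05 level for efficacy analyses, and 7.3.2.2 sets no other yardstick for the sensitivity result.

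**The concern.** The primary MMRM relies on MAR. For the continuous endpoints themselves, this MI is the planned analysis that departs from that assumption; the per-protocol repeat changes the population instead. With no other criterion stated, readers will compare its p-value with 0.05. A pooled result from a finite number of imputations varies from one set of draws to another, and at m = 20 that variation can move a borderline p-value across 0.05. The same choice of m governs the check on all four confirmatory endpoints. What is at stake is whether a borderline sensitivity result supports or questions the main analysis for a reason unrelated to the trial data.

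**Working it through.** **Inputs.** m = 20 (SAP 7.3.2.2). Two-sided alpha 0.05, difference 12 mm, SD 30 mm, dropout 15%, power 90%, 160 per arm (SAP 2.6). FMI is not in the documents. I assume 0.10 to 0.25, a range that contains the planned 15% dropout.

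**1. The plan's own figure.** n per arm = 2 × (1.960 + 1.282)² × (30/12)² = 131.3, so 132. Allowing for dropout, 132/0.85 = 155.3, so 156 per arm or 312 in total. The t-test version gives 133, then 157, or 314 in total. The planned 320 is reproduced to within 3%.

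**2. Scale.** Completers per arm: 160 × 0.85 = 136. Standard error of the difference: 30 × √(2/136) = 3.64 mm. At 12 mm, z = 12/3.64 = 3.30, p about 0.001.

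**3. Monte Carlo error.** The between-imputation variance is B = FMI × T, where T is the total variance. The pooled estimate has Monte Carlo variance B/m, so the Monte Carlo SD of z is √(FMI/m). In mm at m = 20: 3.64 × √(0.10/20) = 0.26, rising to 3.64 × √(0.25/20) = 0.41.

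**4. Chance of crossing 0.05.** Take a p-value of 0.04 at unlimited m, so z = 2.054. Simple formula: Φ((1.960 − 2.054)/√(FMI/m)). The Rubin columns are simulated and add the noise in B, the (1 + 1/m) inflation and Rubin degrees of freedom.

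| FMI | SD(z), m = 20 | simple | Rubin | SD(z), m = 100 | simple | Rubin |
|---|---|---|---|---|---|---|
| 0.10 | 0.071 | 9% | 13% | 0.032 | 0.2% | 0.4% |
| 0.15 | 0.087 | 14% | 20% | 0.039 | 0.8% | 2% |
| 0.20 | 0.100 | 17% | 25% | 0.045 | 1.8% | 4% |
| 0.25 | 0.112 | 20% | 29% | 0.050 | 3.0% | 7% |

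Error also runs the other way. At FMI 0.15 with Rubin pooling, an exact p of 0.055 shows as below 0.05 in about 31% of m = 20 runs, against about 16% at m = 100.

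**5. Away from the boundary.** For an exact p of 0.03 the simple formula at m = 20 gives 0.2% to 3.0%. For p = 0.01, z = 2.576. The gap to 1.960 is 0.616, or 5.5 Monte Carlo SDs even at FMI 0.25, so the chance is effectively zero.

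**6. Averaged over trials.** Draw the exact z from a normal distribution with mean 3.30 and SD 1, then add the m = 20 error. The two answers fall on different sides of 0.05 in about 0.9-1.5% of trials by the simple formula (FMI 0.10 to 0.25), and in 1.0-2.2% with Rubin pooling (FMI 0.10 to 0.30). If the effect in the sensitivity analysis were nearer the boundary, at 7.2 mm, the figure is 2.5-5.1% (FMI 0.10 to 0.30).

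**7. How far a larger m helps.** For an exact p of 0.045, z = 2.005 and the gap is 0.045. At m = 100 the simple formula gives 8%, 12%, 16% and 19% across the four FMI values. At m = 500 the SD of z is 0.014 to 0.022 and the chance is 0.1% to 2.3%. With Rubin pooling at FMI 0.15 the sequence for m = 20, 100 and 500 is 36%, 16.5% and 1.3%.

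The simulations treat the pooled estimate as normal with Rubin-type variance. They do not re-run the actual MNAR/MAR imputation.

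**The case against.** The strongest reply is that nothing in the plan turns on this p-value. The analysis is labelled as sensitivity, the primary test needs no imputation, the gatekeeping passes no alpha through it, and no pass/fail rule is attached to it. Read as an estimate with a confidence interval, a seed-to-seed SD of 0.26 to 0.41 mm is small beside a standard error of 3.64 mm and a design effect of 12 mm. All of this stands, and it is why the point is minor.

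A reader might infer that someone could select a favourable seed. The documents do not support that: Appendix 13.2 lists the seeds, fixes their order and gives an overflow rule. Fixing the seed makes the draw reproducible, but it does not make it more precise.

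A reader might also infer that this MI is the sole check on missing data. It is not. SAP 7.3.3.3 compares 30% and 50% improvement in leg pain with missing counted as failure, and SAP 7.3.3.6 does the same in cumulative plots for leg pain and ODI at Weeks 13 and 52. These are dichotomised or graphical rather than repeats of the MMRM, but they are pessimistic about missing data and involve no seed. Herniation volume has only the MI.

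**Conclusion.** The concern holds as a minor point of precision. Twenty imputations is neither an error nor a contradiction, but it leaves Monte Carlo error that could be removed almost for free. An exact sensitivity p of 0.04 would show as 0.05 or more in about 9-20% of runs by the simple formula, or 13-29% with Rubin pooling, if FMI is 0.10 to 0.25. At the design effect, conclusions differ in roughly 1-2% of trials; clear results are untouched. These sizes rest on the assumed FMI and on the planning SD and dropout. More missing data at Week 52 is plausible because dropout accumulates, but the documents give no figure for it. It should not be inferred that 100 imputations would end the dependence on the draw: any finite m leaves a borderline band, and at p = 0.045 about 8-19% of m = 100 runs would still cross.

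**What to change.** In SAP 7.3.2.2, change the number of imputations, and the matching number of data sets to be pooled, from 20 to at least 100 and preferably several hundred. Pool all of them; 7.3.3.2 follows by reference. The overflow rule in Appendix 13.2 supplies further seeds. If one seed is used per imputed data set, add a clause saying that third and later passes through the list add 2, 3 and so on, since ten seeds and one repeat cover only 20. Report the Monte Carlo error of the pooled estimate, √(B/m), next to the estimate and its confidence interval. The cost is two numbers and a sentence in the SAP plus some computing time. The estimand, the imputation model and the error rate do not change.

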7.3.2.3 Per Protocol Analyses

The primary analysis and the key secondary analyses will be repeated on the PP population.

7.3.2.4 Comparison of Results in Subpopulations

Analyses for the primary endpoint will be conducted for the mITT Population on the following subgroups:

- Age categories: 20-29 years, 30-49 years, 50-59 years and ≥ 60 years (only study 6603/1031 includes 20-29 group, but will be reported and discussed in the ISE text)
- Sex: Male, Female
- Race: White, Black or African American, Asian, and Other.
- Ethnicity: Hispanic or Latino, Not Hispanic or Latino (applies to Study 6603/1133 only)
- BMI categories: $<18.5 \text{ kg/m}^2$, $18.5 \text{ to } < 25.0 \text{ kg/m}^2$, $25.0 \text{ to } < 35.0 \text{ kg/m}^2$, and $\geq 35.0 \text{ kg/m}^2$
- Height: $<170 \text{ cm}$, $\geq 170 \text{ cm}$
- Disc level: L4/L5, L5/S1 (subjects that have the procedure on L6 will be grouped with the L5/S1 subjects)

The goal of these subgroup analyses is to explore potential differences in treatment response by subgroup. The analysis and reporting will parallel the primary reporting and MMRM model where possible. If convergence issues arise due to insufficient sample size, then descriptive statistics only may be reported for a subgroup.

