2.6 Sample Size Determination

It is planned to enroll approximately 320 subjects, 160 in the SI-6603 group and 160 in the control group.

Sample size estimation is based on using the mean difference in the worst leg pain score change from baseline in the primary efficacy analysis. The following assumptions were made to compute the sample size:

- The 2-sample t-test comparing the group means of the change from baseline was used. (The 2-sample t-test approximates the test of the null hypothesis based on the repeated measures model that will be used in the primary efficacy analysis.)
- Treatment difference between SI-6603 and control groups of 12 mm
- Common standard deviation (SD) of 30 mm
- Dropout rate of 15%
- Power of 90%
- Two-sided significance level of 5%

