7.3.4 Multiple Comparisons

To control family-wise error rate for multiple tests of the primary and key secondary endpoints, serial gatekeeping testing algorithm will be used.

1. The treatment effect on the primary endpoint will be evaluated at $\alpha = 0.05$.
2. If the effect on the primary endpoint is significant, the treatment effect on the key secondary endpoint of worst leg pain score at Week 52 will be evaluated using $\alpha = 0.05$.
3. If worst leg pain score at Week 52 is significant $\alpha = 0.05$, then the herniation volume at Week 13 will be tested at $\alpha = 0.05$.
4. If the herniation volume at Week 13 is significant $\alpha = 0.05$, then the ODI at Week 13 will be tested at $\alpha = 0.05$.

If at any point in the sequence an endpoint fails to meet significance at $\alpha = 0.05$, then the algorithm will be halted and the remaining tests declared non-significant regardless of their p-values. Endpoints and time points other than those above may have p-values reported, but none of these will be considered to be statistically significant.

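### The subgroup section aims to explore differences in treatment response but specifies no treatment-by-subgroup contrast, interval or heterogeneity test

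*SAP*

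**What the plan says.** SAP 7.3.2.4 lists seven factors for subgroup analysis of the primary endpoint: age, sex, race, ethnicity, BMI, height and disc level. On purpose it says: "The goal of these subgroup analyses is to explore potential differences in treatment response by subgroup". On method it says: "The analysis and reporting will parallel the primary reporting and MMRM model where possible". It adds a fallback: "If convergence issues arise due to insufficient sample size, then descriptive statistics only may be reported for a subgroup".

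The model to be paralleled is in SAP 7.3.2: "The model will include the baseline worst leg pain score, treatment, time, treatment-by-time interaction, and duration of leg pain as fixed effects". Its covariance is unstructured over eight visits, with compound symmetry if the unstructured fit does not converge. The summary measure is the Week 13 difference in least-squares means (SAP 7.3.1), and Protocol 11.8.3 makes two-sided 95% intervals the default.

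Protocol section 11 plans no subgroup analysis, so SAP 7.3.2.4 is the only governing text. Neither document mentions a treatment-by-subgroup term, a contrast between levels, an interval for a difference in effects or a test of heterogeneity.

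**The concern.** The aim is comparative, but the method is not. An effect estimated within men and another within women do not, as displayed, tell the reader how far the two effects differ or how uncertain that difference is. Without that estimate, readers tend to compare a nominally significant level with a non-significant one. That comparison is not evidence of a difference, and in a trial powered only for its overall effect such patterns are common by chance.

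There is also a question of comparability. An unstructured covariance over eight visits has 8 × 9 / 2 = 36 parameters, to be estimated afresh in each level under separate fits. One level of a factor could be reported from an unstructured fit, another from compound symmetry and a third from descriptive statistics alone. Those results do not sit on the same footing, and a level with descriptive statistics only has no model-based effect to set against the others.

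**Working it through.** **Inputs.** SAP 2.6 gives: "Treatment difference between SI-6603 and control groups of 12 mm"; "Common standard deviation (SD) of 30 mm"; two-sided 5% level; 90% power; 15% dropout; 160 per arm. Subgroup prevalence is in neither document, so the splits below are assumptions.

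**The plan's own figure.** n per arm = 2 × (1.960 + 1.282)² × (30/12)² = 131.3, so 132. Dividing by 0.85 gives 156 per arm, 312 in total. An exact t-test gives 133, then 157 per arm, 314 in total. Both agree with the planned 320 or so. Evaluable subjects: 160 × 0.85 = 136 per arm, with power of 91% for the overall effect.

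**Formulas for a two-level factor.** With n_k evaluable subjects per arm in level k:
- SE_k = 30 × √(2/n_k)
- power in level k ≈ Φ(12/SE_k − 1.96)
- chance that exactly one level is nominally significant = p₁(1 − p₂) + p₂(1 − p₁), because the levels contain different subjects
- SE of the between-level difference = √(SE₁² + SE₂²)

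**50/50 worked through.** n_k = 68, so SE_k = 30 × √(2/68) = 5.14 mm. Power = Φ(2.33 − 1.96) = 64.5%. Exactly one significant: 2 × 0.645 × 0.355 = 0.458. SE of the difference = 5.14 × √2 = 7.28 mm; 95% half-width 1.96 × 7.28 = 14.3 mm.

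**Results when the true effect is 12 mm in both levels:**

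| Assumed split | Power in each level | Exactly one significant | SE of difference | 95% half-width |
|---|---|---|---|---|
| 50/50 | 64.5%, 64.5% | 46% | 7.3 mm | 14.3 mm |
| 70/30 | 79%, 44% | 54% | 7.9 mm | 15.6 mm |
| 90/10 | 88%, 18% | 74% | 12.1 mm | 23.8 mm |

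For comparison, the overall effect has SE 30 × √(2/136) = 3.64 mm and half-width 7.1 mm. If all 160 per arm contributed, the chance of exactly one significant level would be 41% at 50/50 and 50% at 70/30, so the pattern does not depend on the dropout assumption.

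**What the missing contrast could show.** If the effects truly differed by 12 mm, power would be Φ(12/7.28 − 1.96) = 38% at 50/50 and 33% at 70/30. Power of 80% needs a difference of about (1.960 + 0.842) × 7.28 = 20.4 mm at 50/50, or 22.2 mm at 70/30.

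**The case against.** The other side has several good arguments, and most of them limit the point rather than remove it.

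- A reader might infer that the plan yields only a p-value per subgroup. The documents do not support that. Paralleling the primary reporting gives a Week 13 least-squares mean difference for each level, with a 95% interval by default. For a two-level factor a reader could subtract the two estimates and combine their standard errors. What is missing is a planned and displayed contrast. The subtraction is unavailable where a level has descriptive statistics only.
- A reader might infer that the SAP expects some subgroup fits to fail. Its wording is conditional, and SAP 7.3.2 puts compound symmetry between the unstructured fit and descriptive statistics.
- The SAP never says that separate models will be fitted. That is inferred from the unchanged primary model and from a convergence fallback that applies to a single subgroup. It is the natural reading, but an inference.
- The list mentions another study and integrated-summary text, so comparisons between subgroups may be planned elsewhere. No such plan is among the documents, and it would not supply the contrast for this trial's own report.
- The analyses are exploratory. SAP 7.3.4 says: "Endpoints and time points other than those above may have p-values reported, but none of these will be considered to be statistically significant". That sentence covers endpoints and time points and does not name subgroups. Even read broadly, it withholds a claim of significance and does not provide the estimate that the section sets out to explore.
- The contrast will be imprecise. That is true, and it is a reason to show its interval rather than leave readers to judge by eye.

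**Conclusion.** The point holds as a gap between the stated aim and the specified method. On the arithmetic above, when no true difference exists, one significant and one non-significant level is roughly as likely as not at 50/50 to 70/30 splits. The between-level standard error is about twice that of the overall effect (7.3 to 7.9 mm against 3.64 mm). These figures assume the splits, an equal 12 mm effect, a normal approximation with SD 30 mm, and two-level factors. They do not describe age, race or BMI, which have more than two levels.

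It would be a mistake to read this as a threat to the trial's main result. The primary test, the sample size and the gatekeeping sequence do not depend on the subgroup section. The point bears only on how exploratory subgroup results can be interpreted, and it ranks as a cheap improvement.

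**What to change.** For each factor, fit one MMRM on the full mITT population. Add subgroup, subgroup-by-time, treatment-by-subgroup and treatment-by-subgroup-by-time terms to the primary model, with a common covariance matrix. From that model report the Week 13 effect in each level and the between-level difference with its 95% CI, labelled exploratory.

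For factors with more than two levels, give a global Week 13 interaction test plus contrasts against a stated reference level. Pre-specify how sparse levels will be pooled. Pooling the model eases estimation but does not guarantee it: a four-level factor still needs 4 × 2 × 8 = 64 cell means, and a level with no subjects in one arm at Week 13 has no estimable effect.

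The cost is a few lines of SAP text and a small change to the model code, with no new data. The downside is the assumption of a common covariance across subgroups. The resulting contrast will also be wide, and the report should say so.

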7.3.3 Secondary Efficacy Analyses

7.3.3.1 Key Secondary

A longitudinal analysis model will be used as described in the primary efficacy analysis for the analyses of change from baseline in the herniation volume at Week 13, change from baseline in the worst leg pain score at Week 52, and change from baseline in the ODI at Week 13. The baseline value of each outcome will be included as a covariate in these models in place of the baseline worst leg pain score (from the primary analysis). Note that herniation volume is collected only at Weeks 13 and 52; ODI assessment shares the same time points as the primary.

Key secondary endpoints will be summarized by treatment group and time point. Mean change from baseline in key secondary endpoints over time will be summarized in a line

graph with error bars. Estimated value in key secondary endpoints over time will be summarized in a line graph with 95% confidence interval (CI) displayed.

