*Conservative treatment is pharmacotherapy (e.g., steroids, NSAIDs, or non-opioid analgesics), physical therapy, chiropractic, acupuncture, spinal injection, epidural injection, or nerve block. For spinal injection, an inadequate response over a 4-week period can be counted toward the required \geq 6 weeks of conservative treatment.

6. Subjects whose worst leg pain (100 mm VAS) for the 7 consecutive days up to the day before randomization meets following conditions:

- a. worst leg pain scores have been recorded for at least 5 out of the 7 days;
- b. the mean of the worst leg pain scores is 50 to 90 mm; and
- c. the range of fluctuation in worst leg pain scores over the 7 days (difference between minimum and maximum scores) is \leq 25 mm.

7. Subjects who can comply with the rules of concomitant medications (See Section 6.6) and therapies (See Section 6.7) usage as defined in the protocol.
8. Subjects who can comply with the rules of rescue medication usage as defined in the protocol (See Section 6.6.4) and, for those who qualify to receive rescue medication 2 (hydrocodone/acetaminophen), are not at high risk of opioid abuse, as determined by the investigator.
9. Subjects with \geq 30% on the ODI at the time of randomization.

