9.2.2 Visit 2: Randomization (Day -1 or Day 1)

The following activities will be performed on the day before (Day -1) or the day of (Day 1) investigational product administration.

Before randomization:

- Complete the ODI, SF-36, EQ-5D-5L, and WPAI assessments.
- Collect concomitant medication and therapy information.
 - Confirm use and amount of concomitant medication(s)/therapy(ies).
 - Assess use of restricted medication(s)/therapy(ies) for LDH.
 - Confirm washout of prohibited medications.
 - Confirm rescue medication use.
- Collect vital signs.
- Record AEs.
- Perform neurological examination.

- Perform urine drug test.
- Perform urine pregnancy test (for women of childbearing potential).
- Confirm that the subject meets all of the inclusion criteria and none of the exclusion criteria and is therefore eligible to participate in the study.

Randomization:

Randomization must occur within screening period or on the day of investigational product administration (Day 1).

- Randomize subject to SI-6603 or sham injection once all screening assessments are complete.

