3.1 Baseline values

For visit-based measures, baseline will be the last non-missing value prior to injection. For diary-based measures, the baseline will be the average of the scores for the 7 consecutive days up to the day prior to randomization (independently for worst leg pain and worst back pain). Per the inclusion criteria, subjects should have a minimum of 5 non-missing values; however, if a subject is inadvertently randomized with fewer values, then the baseline will be the mean of the available values from that 7 day period. Note that post-baseline visits were scheduled per the protocol with the injection date as day 1; in rare instances, this may be after the randomization date. In these cases, the baseline will be anchored around the randomization visit. Additionally, in the instance that a subject is inadvertently entered into the randomization system and assigned a kit on a day other than their visit 2A, the anchor date will be the day that they were confirmed to have qualified for the trial (typically the day of visit 2A).

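### Optional small efficiency gain: the herniation-volume and ODI models could keep baseline worst leg pain, and the leg-pain model could add baseline ODI

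*SAP*

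**What the plan says.** SAP 7.3.2 sets out the primary MMRM: "The model will include the baseline worst leg pain score, treatment, time, treatment-by-time interaction, and duration of leg pain as fixed effects". Baseline ODI is not among these terms.

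SAP 7.3.3.1 carries this model over to the three key secondary endpoints: herniation volume at Week 13, and "change from baseline in the worst leg pain score at Week 52, and change from baseline in the ODI at Week 13". It makes one change: "The baseline value of each outcome will be included as a covariate in these models in place of the baseline worst leg pain score". Protocol 11.6.1 and 11.6.2 give the same covariate rules, so the two documents agree. Neither explains why the outcome's own baseline replaces baseline leg pain and is not added to it.

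Both baselines are tied to eligibility. For leg pain, Protocol 4.1 requires that "worst leg pain scores have been recorded for at least 5 out of the 7 days" and that "the mean of the worst leg pain scores is 50 to 90 mm". It also requires an ODI of at least 30% at randomisation. Protocol 9.2.2 lists, among the steps before randomisation, "Complete the ODI, SF-36, EQ-5D-5L, and WPAI assessments". SAP 3.1 covers short diaries: "if a subject is inadvertently randomized with fewer values, then the baseline will be the mean of the available values from that 7 day period".

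**The concern.** Adjusting for a prognostic baseline variable in a randomised trial reduces residual variance and costs about one degree of freedom. Pain severity and disability could each say something about later pain, disability or herniation volume that the other does not. Both are already collected, so leaving one out may give up some precision. The key secondary tests form a serial chain (SAP 7.3.4), with herniation volume third and ODI fourth, and one miss ends the testing.

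The second consideration is missing data. Herniation volume is measured after baseline only at Weeks 13 and 52. Under SAP 7.1.2 a discontinuation MRI counts only if it falls in the window of a visit with scheduled imaging. A subject who leaves at Week 6 therefore contributes no volume outcome, and the volume model contains no pain score at all. Missing at random must then hold given treatment, baseline volume and duration of leg pain alone.

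**Working it through.** **Which models are affected**

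| Model | Own baseline | Baseline leg pain in model? | Baseline ODI in model? |
|---|---|---|---|
| Leg pain, Week 13 (primary) and Week 52 | leg pain | yes (it is the own baseline) | no |
| Herniation volume, Week 13 | volume | no | no |
| ODI, Week 13 | ODI | no | yes (it is the own baseline) |

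The replacement rule therefore removes leg pain from two of the three key secondary models.

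**The plan's own figure.** Inputs from SAP 2.6: difference 12 mm, SD 30 mm, two-sided 5%, power 90%, dropout 15%, unadjusted two-sample t-test.

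- Normal approximation: n per arm = 2 × (1.960 + 1.282)² × (30/12)² = 131.3, so 132. Divided by 0.85 this is 156 per arm, 312 in total.
- Noncentral t: 133 per arm, 157 after dropout, 314 in total.

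Both agree with the planned total of about 320. With 160 × 0.85 = 136 evaluable per arm, the SE is 30 × √(2/136) = 3.64 mm and the noncentral-t power is 0.908.

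**Effect of one added covariate on the primary.** Let R² be the share of residual variance that it explains beyond the terms already in the model. The documents give no value, so a range is assumed. The SE is multiplied by √(1 − R²), the equivalent increase in sample size is 1/(1 − R²) − 1, and power uses d = 0.4/√(1 − R²) with 136 per arm.

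| R² (assumed) | SE, mm | SE reduction | Equivalent extra subjects | Power |
|---|---|---|---|---|
| 0 | 3.64 | 0 | 0 | 0.908 |
| 0.01 | 3.62 | 0.5% | 1.0% | 0.910 |
| 0.03 | 3.58 | 1.5% | 3.1% | 0.916 |
| 0.05 | 3.55 | 2.5% | 5.3% | 0.921 |

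The 30 mm starting point takes no credit for covariates already in the model.

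**Why zero belongs in the range.** What matters is the partial correlation after the own baseline: (r₂ − r₁r₁₂)/√((1 − r₁²)(1 − r₁₂²)). Here r₁ is the correlation of the own baseline with the outcome, r₂ that of the other baseline with the outcome, and r₁₂ that between the two baselines. All values below are assumed.

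- r₁ = 0.4, r₂ = 0.3, r₁₂ = 0.5: partial correlation 0.13, SE reduction 0.8%.
- r₁ = 0.5, r₂ = 0.2, r₁₂ = 0.4: partial correlation 0, no reduction.

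**Cost if the covariate is useless.** With 272 evaluable subjects, one more term inflates the variance by about 267/266, which is about 0.2% on the SE.

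**Key secondary endpoints.** The documents give no effect size or SD for herniation volume, ODI or Week 52 leg pain, so their power, with or without the extra covariate, cannot be computed.

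**The case against.** Adjusting for the outcome's own baseline is a legitimate, pre-specified choice, stated identically in protocol and SAP. It causes no bias and no type I error problem. The design reaches its 90% target on an unadjusted test that takes no credit for covariates. Almost any trial could be told to add one more baseline term. Eligibility also narrows both measures (leg pain 50 to 90 mm, ODI at least 30%), which limits what either can explain. All of this stands, and it is why the point is optional.

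Three stronger readings are tempting, and the documents do not support them.

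- *All key secondary models lose baseline leg pain.* The Week 52 leg-pain model keeps it.
- *Precision is demonstrably lost.* No correlation is given, and the gain can be zero.
- *Drop-out is driven by pain, so the omission threatens missing at random.* The documents give a 15% dropout assumption and a varied list of discontinuation reasons (SAP 5.1). Protocol 5.1 and 6.7.1 do link withdrawal to poor response, but that concerns pain after injection, which baseline pain may reflect only weakly. The ODI model already conditions on ODI from Week 1 onward. SAP 7.3.2.2 and 7.3.3.2 add a multiple-imputation analysis, not at random for lack of efficacy, adverse events and treatment failure. Some force remains for herniation volume only, which has no early post-baseline visit.

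**Conclusion.** The point holds as a small, nearly free efficiency improvement. The volume and ODI models drop baseline worst leg pain, and the leg-pain model omits baseline ODI, although both should be on record before randomisation for essentially every subject.

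On the primary, the gain is 0.2 to 1.3 percentage points of power (0.908 to between 0.910 and 0.921) if the added covariate explains 1% to 5% of residual variance, and nothing if it explains none. These percentages are assumptions. For volume and ODI only the proportional SE reduction for a given R² carries over. For volume, conditioning on baseline pain may also make missing at random somewhat more plausible, but it does not secure it. A reader should not infer that the planned analysis is invalid or the trial underpowered.

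**What to change.** If the sponsor takes this up, it should be settled before unblinding:

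1. In SAP 7.3.3.1, state that the herniation-volume and ODI models each include the outcome's own baseline and baseline worst leg pain, each entered once, with the other terms unchanged.
2. In SAP 7.3.2, add baseline ODI to the worst-leg-pain model that serves both Week 13 and Week 52.
3. Record both changes in SAP section 11, because they depart from the covariate sets in Protocol 11.6.1 and 11.6.2.

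The covariates should be listed model by model. Merely turning the replacement rule into an addition rule would enter leg pain twice in the Week 52 leg-pain model. With ODI added to 7.3.2, it would also enter ODI twice in the ODI model and carry it unannounced into the volume model. SAP 7.3.3.3 uses the same replacement rule for function scores and volumes, and should be aligned so that ODI and herniation volume at Week 13 are not estimated from two different models.

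The cost is SAP wording, a declared departure from the protocol's primary covariates, and about one degree of freedom per added covariate. If only one change is made, keeping baseline leg pain in the volume model has the clearest rationale.
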